Primary analysis will verify balance in matching (unadjusted) via Chi-squared model for binary variables and ANOVA for categorical variables

I. Engagement Analyses: Overall engagement by patients in the intervention arm with the Wellframe application will be assessed by evaluating the number of days or weeks with at least one task completed (including surveys done, content read, activity goals reached and medication reminders used) within both a 30- and 90-day period. Individual task completion rates will also be assessed and reported within 30- and 90-day periods. Use of messaging between patients and health advocates will also be assessed during a 30- and 90-day period. Changes in these metrics across 30- to 90-days will be evaluated.

J. Exploratory Analyses:

We will compare subgroups (MI/elective) using linear regression across the 30-day engagement metrics above to evaluate predictors of engagement (adjusting for both 30-day engagement as well as matching covariates such as age, sex, PCI type, state, insurance, partners PCP and site).

We will use the Cox Proportional Hazards model to assess efficacy of the intervention on lowering rate of ER visits for cardiovascular reasons, ER visits for all causes and hospitalizations for all reasons.

We will use the Cox Proportional Hazards model to assess efficacy of the intervention on reducing rates of repeat PCI, stroke, non-fatal MI, cardiovascular cause of death and all cause death within 90 days of enrollment.

We will use the Cox Proportional Hazards model to assess for improvement in percentage of patients adhering to cardiovascular follow up appointments within 30 days of discharge.

K. Type I Error Control: We will control for error by limiting our primary outcome to 90-day cardiac rehabilitation enrollment. All subsequent analysis, including secondary outcomes, will be considered exploratory.

L. References:

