% of patients who attend at least one clinic-based cardiology follow up appointment within 4 weeks of discharge.

Outcome	Exposure(s)	Tables
OP CV F/U	Wellframe	
OP CV F/U	Wellframe + age + sex + insurance + state + DM2 + Partners PCP	

4. Comparison of Exploratory Outcomes:

30D Outcomes: All Cause Hospital, CV Hospital, All Cause ER, CV ER, CV FU and CR

A. 30 day readmission (All cause) (Cox Proportional Hazards Model)

Outcome	Exposure(s)	Tables
All Cause 30d	Wellframe	
All Cause 30d	Wellframe + age + sex + insurance + state + DM2 + Partners PCP	

B. 30 day readmission (CV related) (Cox Proportional Hazards Model)

Outcome	Exposure(s)	Tables
CV 30d	Wellframe	
CV 30d	Wellframe + age + sex + insurance + state + DM2 + Partners PCP	

C. MACE (Cox Proportional Hazards Model)

Outcome	Exposure(s)	Tables
MACE	Wellframe	
MACE	Wellframe + age + sex + insurance + state + DM2 + Partners PCP	

D. 90 day readmission (All cause) (Cox Proportional Hazards Model)

Outcome	Exposure(s)	Tables
All Cause 90d	Wellframe	
All Cause 90d	Wellframe + age + sex + insurance + state + DM2 + Partners PCP	

E. 90 day readmission (CV related) (Cox Proportional Hazards Model)

Outcome	Exposure(s)	Tables
CV 90d	Wellframe	
CV 90d	Wellframe + age + sex + insurance + state + DM2 + Partners PCP	

4. Engagement (Data from Wellframe)

Table 4.1

	90-day
Conversion Rate	
Enrolled/Total PCI	%
Enrolled/Approached	%
Average Days Enrolled	##
Average Medication Reminders	##
Average Patient Satisfaction	##
Average Clinical Messages	%
Average Days to First Message	##
Average Patient Messages Received	##
Average Patient Messages Opened	%
Average Patient Message Response	%
Average Patient Messages Sent	##
Average Patient Physical Activity	%

i. Conversion Rate (# pt enrolled in Wellframe out of # eligible)

- a. Percentage of patients enrolled / total PCI
- b. Percentage of patients enrolled / approached

Table 4.2

	30-day	90-day
Medication Adherence	%	%
Content Completion	%	%
Survey Completion	%	%
Weekly Patient Engagement	%	%
Daily Patient Engagement	%	%

Table 4.3: Predictors of Engagement: Pearson Correlation Analysis

Outcome	Exposure(s)	Figure
Daily Engagement 30d	Age + Sex + DM2 + knownCAD + HTN + HLD + MI/Elective + PAD	Correlation Matrix
Daily Engagement 90d	"	
Weekly Engagement 30d	"	
Weekly Engagement 90d	"	

Table 4.4: Sentiment Analysis (what the messages are about)

Table 4.5: Matrix of correlation between the different engagement values given by Wellframe

FIGURES:

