1. Cardiac Rehabilitation Enrollment: Bar Plot (Intervention Group vs Control Group)
2. App Engagement: Bar Plot (Percentage of Days With App Engagement)
3. Outpatient Cardiac Follow Up: Bar Plot (Intervention Group vs Control Group)
4. 30-Day and 90-Day Readmission Rates: 2 Panel Bar Plot (Intervention Group vs Control Group)
5. App/Dashboard Representative Image (From Wellframe)
6. Process Outcomes: Flow chart of recruitment/enrollment.
7. Daily Engagement and Clinical Outcomes [CR Enrollment, CVFU, 30 Day Readmission, 90 Day Readmission]: 4 Panel Bar Plot (Intervention Group vs Control Group)
8. Predictors of Engagement: Correlation Matrix (Daily/Weekly Engagement Rates vs Traditional CV Risk Factors [Age, Sex, Known CAD, MI, PAD, DM2, HTN, HDL])

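### The SAP gives two unreconciled analyses for predictors of app engagement, and neither, as written, gives an age-adjusted estimate for hypertension, hyperlipidemia, PAD or known CAD

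*SAP*

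**What the plan says.** **SAP Section J (Exploratory Analyses):** "We will compare subgroups (MI/elective) using linear regression across the 30-day engagement metrics above to evaluate predictors of engagement". The adjustment is described in brackets: "adjusting for both 30-day engagement as well as matching covariates such as age, sex, PCI type, state, insurance, partners PCP and site". The words introducing the covariates leave the list open, but only to matching covariates.

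**SAP output shells, engagement section:** "Table 4.3: Predictors of Engagement: Pearson Correlation Analysis". The exposure column reads "Age + Sex + DM2 + knownCAD + HTN + HLD + MI/Elective + PAD", the output column asks for a correlation matrix, and the outcomes are daily and weekly engagement at 30 and 90 days, the last being "Weekly Engagement 90d".

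**SAP figure list, item 8:** "Predictors of Engagement: Correlation Matrix (Daily/Weekly Engagement Rates vs Traditional CV Risk Factors [Age, Sex, Known CAD, MI, PAD, DM2, HTN, HDL". The factors are those of Table 4.3, except that the last is printed HDL where the table has HLD.

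Section E.1.b defines the engagement population as intervention subjects who downloaded the app. Section K makes everything other than 90-day cardiac rehabilitation enrollment exploratory.

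**The concern.** One label covers two analyses that differ in method (adjusted regression against pairwise correlation), in variables, and in time window (30 days against 30 and 90 days). Nothing in the SAP says whether one replaces the other or both will be run, so that choice could be made after the results are seen.

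The second difficulty is confounding by age. Enrollment spans ages 21 to 85. A pairwise Pearson correlation takes one factor at a time and cannot remove age. Hypertension, hyperlipidemia, PAD and known CAD plausibly rise with age, and app use may vary with age. If both hold, each factor's raw correlation carries part of the age effect and would be displayed under a title that calls it a predictor.

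The protocol's expected-benefits section looks to this study to inform later work on patients' use of mobile health apps. A table that mistakes age for a comorbidity would be a poor guide for that.

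**Working it through.** The documents state no effect size, power or threshold for this analysis, so there is no figure of theirs to reproduce. The check has two parts.

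**1. Variable lists side by side**

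| Variable | Named in Section J | Table 4.3 |
|---|---|---|
| Age, sex, PCI type (MI/elective) | yes | yes |
| State, insurance, Partners PCP, site | yes | no |
| DM2 | no, but a matching variable in D.2.b | yes |
| Known CAD, HTN, HLD, PAD | no, and not matching variables in D.2.b | yes |

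Three variables are shared, four are named only in Section J, and five only in Table 4.3. Section J's open list could take in DM2, because DM2 is a matching variable. It does not reach the other four. So if both analyses are run exactly as written, those four factors get a raw correlation and no age-adjusted estimate.

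**2. How much could age alone produce?**

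Inputs: n = 150 (planned enrollment, SAP D.8; the number of downloaders may differ) and a two-sided 5% test. D.8 gives alpha 0.05 for the primary outcome only, so its use here, and the two sides, are assumptions. The age correlations are also assumptions; the documents give none.

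If a factor is related to engagement only through age, its raw correlation has absolute size

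r = |r(age, engagement)| × |r(age, factor)|.

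By Fisher's z, with z = atanh(r) × √(n − 3) and √147 = 12.12,

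P(flagged) = Φ(z − 1.96) + Φ(−z − 1.96).

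Worked case with 0.3 and 0.4: r = 0.12, atanh(0.12) = 0.1206, z = 1.46. Then Φ(−0.50) + Φ(−3.42) ≈ 0.31.

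| r(age, engagement) | r(age, factor) | Induced r | P(p < 0.05) |
|---|---|---|---|
| 0.1 | 0.2 | 0.02 | 5.7% |
| 0.2 | 0.3 | 0.06 | 11% |
| 0.3 | 0.3 | 0.09 | 19% |
| 0.3 | 0.4 | 0.12 | 31% |
| 0.4 | 0.4 | 0.16 | 50% |
| 0.4 | 0.5 | 0.20 | 69% |

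The smallest |r| that reaches p < 0.05 at n = 150 is 0.160.

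**Simulation check.** This used 3,000 runs per setting, n = 150, and five binary factors with assumed prevalences of 10% to 75%, each related to engagement only through age. Pearson correlation flagged a given factor 5.6% of the time at 0.1/0.2, 20% at 0.3/0.3 and 70% at 0.5/0.4. A linear regression with age and all five factors flagged a given factor 4.8% to 5.4% of the time in every setting.

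The chance of flagging at least one of the five on a single outcome was 25%, 65% and 99% for Pearson in those three settings. For the regression it was 22% to 24% throughout, which is multiplicity alone.

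**The case against.** The best defence is that these are two complementary exploratory analyses sharing a label. Section J's sentence opens with an MI versus elective comparison and uses the matching variables as adjusters; Table 4.3 screens cardiovascular risk factors. For the descriptive question of who engages, a raw correlation is a legitimate answer, and age sits in the same matrix where readers can see it. This stands in part: nothing shows that the two exclude each other. It does not close the gap, because running both still leaves four factors without adjustment for age under a title that speaks of predictors.

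The plus signs in Table 4.3 could also be read as a multivariable model, since the SAP's Cox shells use them that way. The table's title and output column point to pairwise correlation instead. The SAP should say which is meant.

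A reader might infer three stronger things that the documents do not support:

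- *That risk factors which merely track age will be reported as predictors.* This needs age to be correlated with both engagement and the factor, and a rule for naming a predictor. The SAP gives none of these. At weak correlations (0.1/0.2) the rate is close to nominal.
- *That the adjusted regression will not be reported.* It has no shell, but the shells are not exhaustive. The Cox models for ER visits and the 30- to 90-day change in engagement have none of their own either.
- *That this is the trial's only evidence on who uses the app.* The protocol collects demographics of those screened for recruitment analyses, and the SAP reports conversion rates and a recruitment flow chart.

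**Conclusion.** The point holds as a gap in specification. The SAP uses one label for an adjusted regression and for unadjusted correlations on a different variable set, does not relate them, and as written leaves hypertension, hyperlipidemia, PAD and known CAD without an age-adjusted estimate. Factors that only track age may therefore appear as predictors of engagement.

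The size is illustrative: about 6% to 69% per factor over the assumed correlations, against about 5% once age is in the model. It rests on n = 150, a two-sided 5% test and correlations that the documents do not supply.

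Two adjacent defects are plain on the page. Section J adjusts for 30-day engagement while 30-day engagement metrics are the outcome, and Figure 8 and Table 4.3 disagree on HDL and HLD.

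Because Section K makes this work exploratory and it does not bear on the primary outcome, the priority is low.

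**What to change.** - In Section J and Table 4.3, specify one multivariable linear regression for each of four outcomes: daily and weekly engagement at 30 and at 90 days. Enter age, sex, PCI type (MI/elective), DM2, known CAD, HTN, HLD, PAD, state, insurance, Partners PCP and site together, and report coefficients with 95% confidence intervals.
- Remove 30-day engagement from the adjusters whenever a 30-day engagement metric is the outcome.
- Keep the Figure 8 matrix, but label it as unadjusted correlations.
- Reconcile HDL in Figure 8 with HLD in Table 4.3.

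The cost is SAP wording and one model table from data already held. The statistical price is wider intervals: eleven single-coefficient variables plus three for the four insurance categories make 14 parameters besides the intercept, in about 150 patients. Adjustment does not deal with multiplicity: with five null factors, at least one was still flagged on a given outcome 22% to 24% of the time. The results should therefore be read as estimates with intervals, not as a list of significant factors.
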